This document contains the statistical analysis plan for 'The POCUS IN PRACTICE study Implementation of point-of-care ultrasonography in general practice: A stepped wedge cluster randomized trial'. The aim is to clarify analyses for the intended analyses. Therefore, the statistical analysis plan has been completed prior to the completion of the data collection. The overall purpose is to estimate the effect of a POCUS intervention for general practitioners. In the primary research article, the following outcomes are reported.

The primary outcomes are:

- (P1) The number of registered reimbursement codes sent by the participating GP.
- (P2) The number of referrals send to secondary care by the participating GP.

The secondary outcomes are:

- S1. The number of consultations in primary care (e-mail, telephone, video, visits) managed by the participating GP.
- S2. The GPs' perceived stress (Cohen's 10-item Perceived Stress Scale)
- S3. The GPs' job satisfaction (Warr-Cook-Wall Job satisfaction Scale)
- S4. The GPs burnout symptoms (Maslach Burnout inventory)
- S7. To describe the number of adverse events reported by the participating GPs following the intervention

The tertiary outcome is:

- T3. GPs' experiences of POCUS' influence on perceived stress, job satisfaction and burnout symptoms after the intervention.

The analysis intended for outcomes S5, S6, S8, T1 and T2 will not be specified in this statistical analysis plan, as these outcomes will be specified in elaborating study protocols and reported in separate articles.

The study design involves random and sequential crossover of clusters from control to intervention until all clusters are exposed (1). Participants (General Practitioners) have been recruited from 24th June 2022 to 1st September 2022 representing all five Danish regions. The GPs have been randomized to receive an education at different time-points.

2. Background of the trial

Increased longevity results in more patients with a higher burden of disease and disability. These patients are complex to handle which increases the future need of healthcare services. Simultaneously, hospitals are becoming increasingly specialized and centralized with patients' length of stay shortened leading to a shift in healthcare services from hospitals to primary care. The general practitioner (GP) must therefore handle more complex patients, finalize the examination and treatment of more patients, and therefore GPs need the capabilities to refer to the correct sub-specialized department. This renders the diagnostic capacity and precision in the GP's office increasingly important. Point-of-care ultrasonography (POCUS) may be of benefit in this regard. We have previously developed an intervention to support GPs in performing POCUS. All participants will receive the educational intervention through attendance of a ultrasound course arranged by PLO-e (The organization of Danish General Practitioners). The educations intervention consists of three teaching seminars delivered over three months, a curriculum of 10 POCUS applications, an online learning platform providing educational support before, during, and after the teaching sessions. The online platform includes videos demonstrating the performance of POCUS, suggestions for additional literature, assignments

to support the development of skills, self-quizzes to focus attention of learning outcomes and specific action cards for each of the 10 POCUS applications framing the examinations in the clinical context. In addition, the online platform provides participants access to webinars and communication with other participants and teachers. The intervention is further described in the research protocol (ClinicalTrials.gov ID NCT05696821).

2.1. Eligibility

All GPs working in Danish general practice will be invited to participate in the study by newsletter invitation circulated by PLO to all PLO members. The newsletter will contain a link to a questionnaire in which the GPs will be asked to specify their name, practice, location of practice (region in Denmark), distance to nearest ultrasound scanning service, whether or not they are already using POCUS, whether or not they will have access to an ultrasound device during the educational intervention, and whether or not they are willing to share data. There will be a deadline (September 1st 2022) for responding to the invitation.

Following the deadline for signing up to participate in the study, the GPs reply to the questionnaires will be screened according to the inclusion and exclusion criteria to make a list of eligible participants fulfilling all inclusion and none of the exclusion criteria

Inclusion criteria:

1. GP, i.e., be a postgraduate medical doctor with a specialization in general practice
2. Work in office-based general practice in Denmark
3. Have access to an ultrasound device in the practice during the study period

Exclusion criteria:

1. GPs with a possible conflict of interest (e.g., industry affiliation related to the use of ultrasound)
2. No signed informed consent to participate.

All patients seen in general practice, that the GPs find relevant to examine with POCUS can be used in the data collection.

3. Adherence

Teachers at the educational intervention will support adherence to research protocols. The teacher will act as mentors for the participants during the educational intervention. The research team will reach out to participants who fail to submit data (GP questionnaires) but otherwise refrain from influencing practice.

4. Baseline characteristics

Tables of summary statistics will be produced in one group. The table will include:

The following participant characteristics will be collected in a baseline questionnaire:

Variable	Unit	Description
Age	years	Mean (SD ¹) and median (IQR ²)
Sex	male, female, other	frequency (%)
Experience as a medical doctor	years	Mean (SD) and median (IQR)
Experience as a GP ³	years	Mean (SD) and median (IQR)
Experience with POCUS ⁴	years	Mean (SD) and median (IQR)
Previous POCUS training	course participation, training during residency, experience from employment within another medical specialty, ad hoc training by colleague, other, no previous training	frequency (%)
Type of practice	solo-practice, partnership practice, solo-practice in collaboration, partnership practice in collaboration, other	frequency (%)
Location of practice	rural, city, mixed	frequency (%)
Distance to radiology department	kilometer	Mean (SD) and median (IQR)
Region	North Denmark Region, Central Denmark Region, Region of Southern Denmark, Region Zealand, Capital Region of Denmark	frequency (%)
Number of GPs working in the practice	1-20	Mean (SD) and median (IQR)
Number of patients listed with the clinic	1000-20000	Mean (SD) and median (IQR)

Note: The number of missing for each variable will be reported. ¹ Standard Deviation, ² Inter Quartile Range, ³ General Practitioner, ⁴ Point Of Care Ultra Sound

Characteristics of scanned patients

We will summarize the age and gender of patients being examined with ultrasound during the study according to the scanning-specific remuneration code being used.

5. Outcomes

Following the use of POCUS in the general practice consultations the GPs will follow normal procedures for registration of activities in general practice using remuneration codes, fee-specific codes for using POCUS, and referrals in the medical record system. Prior to this study 11 fee-specific codes for 10 different POCUS examinations and one code for 'any other' POCUS examination will be installed in the medical record system.

For the data analysis of individual GPs activities (P1, P2 and S1), we will receive the number of monthly remuneration codes and referrals for each participating GP from October 2022 to June 2024.

For the data analysis of the GP questionnaires (S2, S3 and S4), we will include only GPs who have responded to both the BEFORE and AFTER questions related to the outcomes.

5.1. The primary outcomes

Outcome P1:

The number of monthly scanning-specific remuneration codes will be summarized for each participating GP from October 2022 to June 2024. In a stepped wedge analysis model, we will compare the number of scanning-specific remuneration codes BEFORE the intervention to the number of scanning-specific remuneration codes AFTER the intervention.

In addition, we will report the overall frequency of participating GPs, who use the scanning-specific remuneration codes in the end of the study (May and June 2024).

Outcome P2:

The number of monthly referrals will be summarized for each participating GP from October 2022 to June 2024. In a stepped wedge analysis model, we will compare the number of referrals sent by participating GPs BEFORE the intervention to the number of referrals sent AFTER the intervention.

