Secondary sponsor(s)	Novo Nordisk Foundation The General Practice Foundation in Denmark
Contact for public queries	[name] [contact]
Contact for scientific queries	[name] [contact]
Public title	The POCUS IN PRACTICE study
Scientific title	Implementation of point-of-care ultrasonography in general practice: A stepped wedge cluster randomized trial
Countries of recruitment	Denmark
Health condition(s) or problem(s) studied	The use of point-of-care ultrasonography (POCUS) in general practice
Intervention(s)	An educational intervention consisting of three teaching seminars over three months, a curriculum of 10 point-of-care ultrasound (POCUS) applications, an online learning platform providing educational support before, during and after the teaching sessions.
Key inclusion and exclusion criteria	Inclusion criteria: 1. GP, i.e. postgraduate medical doctor with a specialization in general practice 2. Work in office-based general practice in Denmark 3. Access to an ultrasound device in the practice during the study period Exclusion criteria: 1. GPs with a possible conflict of interest 2. No signed informed consent to participate.
Study type	A stepped wedge cluster randomized trial
Date of first enrolment	Expected: January 2023
Target sample size	Two hundred general practitioners
Recruitment status	Has started
Primary outcome(s)	(P1) To estimate the effect of a POCUS intervention for primary care clinics on the number of registered reimbursement codes. (P2) To estimate the effects of a POCUS intervention for primary care clinics on the number of referrals sent to secondary care specialists.

Key secondary outcomes	
We will estimate if POCUS leads to change in:
 
S1. Number of consultations in primary care (e-mail, telephone, video, visits) S2. GPs' perceived stress (Cohen's 10-item Perceived Stress Scale) S3. GPs' job satisfaction (Warr-Cook-Wall Job satisfaction Scale) S4. GPs burnout symptoms (Maslach Burnout inventory) S5. Healthcare costs
 
And in addition, we will evaluate:
 
S6. Patients experiences following POCUS use S7. Adverse events reported by the participating GPs following the intervention S8. The patient pathway and the quality of selected POCUS applications used in general practice

-------------------------------	---

3 Protocol version

Version 5.0 December 27th 2022

4 Funding

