Hypothesis P1: For general practice clinics that receive a POCUS intervention the use of POCUS will increase after the intervention evaluated by comparing the number of registered reimbursement codes before the intervention to the number of reimbursement codes registered after the intervention.

(P2) To estimate the effects of a POCUS intervention for primary care clinics on the number of referrals send to secondary care specialists.

Hypothesis P2: For general practice clinics that receive a POCUS intervention the referral rate (number of referrals to hospital or specialist clinics/number of consultations) will decrease evaluated by comparing the referral rate from before the intervention to the referral rate after the intervention.

Secondary objectives:

We will estimate if POCUS leads to change in:

- S1. Number of consultations (e-mail, telephone, video, GP office, visits)
- S2. GPs' perceived stress (Cohen's 10-item Perceived Stress Scale)
- S3. GPs' job satisfaction (Warr-Cook-Wall Job satisfaction Scale)
- S4. GPs' burnout symptoms (Maslach Burnout inventory)
- S5. Healthcare costs

And in addition, we will evaluate:

- S6. Patients experiences following POCUS use
- S7. Adverse events reported by the participating GPs following the intervention
- S8. The patient pathway and the quality of selected POCUS applications used in general practice

Tertiary objectives:

- T1. GPs' experiences of job contentment before and after the intervention
- T2. GPs' experiences of POCUS use in their practice after the intervention
- T3. GPs' experiences of POCUS' influence on perceived stress, job satisfaction and burnout symptoms after the intervention.

8 Trial design

This is a stepped-wedge cluster randomized trial

[figure not shown]
Study process

This research project has been developed following the Medical Research Council's model for developing and evaluating complex interventions²¹ (Figure 1).

Reporting of this trial will follow international guidelines for reporting²² and protocols will follow the SPIRIT statement²³. Before the inclusion of the first participant, the trial protocols will be registered on clinicaltrials.gov.

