Prior to the present study, we have developed and pilot tested an educational intervention in two preparatory studies. In an effectiveness study (ClinicalTrials.gov Identifier: NCT05274581), we tested if the educational intervention could lead to scanning competence and if scanning competence could be maintained over time. In a cohort study (ClinicalTrials.gov Identifier: NCT05523882), we tested the data collection tools and the implementation of the educational intervention.

Figure 1. Flowchart of the study process

OK 22: Projects included in the 2022 collective agreement between Danish Regions and The Danish Association of General Practitioners.
 OK 25: The 2025 collective agreement between Danish Regions and The Danish Association of General Practitioners, will possibly include a larger scale implementation of POCUS in general practice depending on the results of the OK22 projects.

In this SW-CRT we aim to determine the effects of our intervention by estimating the uptake of the technology by the GPs (outcome P1), change in referral rate (outcome P2), change in number of consultations delivered in primary care (outcome S1), GPs job satisfaction, level of stress, and burn-out (outcomes S2-4), as well as a health economic evaluation (outcome S5). We will also evaluate patient experiences (Outcome S6), advance events and the patient pathway following POCUS use after the introduction of the intervention.

Two-hundred GPs will participate in the study. All participants will be offered the educational intervention (Figure 2). Participants will be randomized to participate in clusters. Each cluster consists of a group of 20 GPs from the same geographical area (the five Danish regions), who receive the educational intervention at a training facility (location) at a given time. The ten clusters will receive the intervention at different timepoints (Figure 2). Hence, the study will include two clusters from each of the five Danish regions, who will receive the educational intervention at a location in the specific region: North Denmark Region (Aalborg or Sæby), Central Denmark Region (Aarhus or Herning), Region of Southern Denmark (Vejle or Odense), Region Zealand (Roskilde or Næstved) and Capital Region of Denmark (København V or Lyngby).

Figure 2. Time schedule for the SW-CRT data collection

year	2022	2022	2022	2023	2023	2023	2023	2023	2023	2023	2023	2023	2023	2023	2023	2024	2024	2024	2024	2024	

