The data management will follow the rules of GDPR and the Danish Data Protection Agency. All study data will be stored on a secure server at Aalborg University. Questionnaire data will be collected using the online platform SurveyXact (Rambøll, Aarhus, Denmark). A data management agreement has been made between Rambøll and Aalborg University. At the end of the data collection, data will be moved from SurveyXact to Aalborg University's server. Register data will be collected by PLSP. Data management agreements between PLSP and Aalborg University will be made prior to the collection of data. PLSP will receive data from the different IT suppliers for the general practice clinics. Data management agreements between the IT suppliers and PLSP as well as the GP clinics and the IT suppliers already exists. For this specific study, we will develop an instruction for the GPs to incorporate in the existing data management agreement prior to the collection of data.

20a Statistical methods for analysing primary and secondary outcomes.

All statistical analyses will be performed using STATA version 17 (StataCorp, Texas, USA).

The principles of Intention-to-treat is followed in the analysis. If a GP e.g. misses one teaching seminar, we will still consider the GP has having completed the educational intervention. Data will be analyzed according to a pre-established Statistical Analysis Plan (SAP) in consultation with a statistician. For the primary outcomes (continuous data), we plan to use linear regression models adjusting for the fixed effect of time and the random effects of clusters.

Due to the nature of the study the intervention cannot be blinded to the participants, but for statistical assessment, data will be blinded as regard to time of collection and location.

20b Methods for any additional analyses (e.g. subgroup and adjusted analyses).

Sensitivity analyses and sub-analyses will be performed to explore the importance of different educational elements in the intervention and background characteristics of participating GPs. These sub-analyses will be defined in the statistical analysis plan.

20c Missing data

A sensitivity analysis will be performed in cases, where missing values are not considered random.

Data monitoring

21a Data monitoring committee (DMC).

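### Hypothesis P2 predicts a fall in referrals per consultation, but P2 is defined and analysed as a number of referrals, so the hypothesis as written has no planned estimate or test

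*SAP*

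**What the plan says.** Four places define P2 as a count:

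- Protocol registration table, primary outcomes: the effect "on the number of referrals sent to secondary care specialists".
- Protocol section 7, P2 objective: the effect "on the number of referrals send to secondary care specialists".
- SAP introduction, list of primary outcomes: "The number of referrals send to secondary care by the participating GP".
- SAP 5.1: "we will compare the number of referrals sent by participating GPs BEFORE the intervention to the number of referrals sent AFTER the intervention".

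Two places speak of a rate:

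- Protocol section 7, Hypothesis P2, directly below the count objective: "the referral rate (number of referrals to hospital or specialist clinics/number of consultations) will decrease".
- Protocol section 8: "change in referral rate (outcome P2", with no denominator given there.

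On analysis, protocol 20a says "For the primary outcomes (continuous data), we plan to use linear regression models" and leaves the detail to the SAP. SAP section 9 applies one linear mixed model to P1, P2 and S1. Its terms are random effects for cluster and GP, fixed step effects, a background time trend and prior POCUS experience. Its sensitivity analyses concern missing data and the time trend.

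**The concern.** The only directional prediction for P2 concerns referrals relative to consultations. The only planned analysis of P2 concerns referrals alone. Carried out exactly as written, the plan would report a primary outcome without estimating the quantity in its own primary hypothesis.

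This matters because the trial itself treats the denominator as something POCUS may alter: the number of consultations is secondary outcome S1. If consultations rise, a true fall in referrals per consultation can be diluted or hidden in the count. If they fall, the count can drop with the rate unchanged. The unreconciled wording also leaves room to choose between count and rate once results are known, which a prespecified plan should rule out.

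**Working it through.** **1. Is a rate analysis planned anywhere?** The documents state no sample size calculation, effect size or baseline for P2, so there is no figure to reproduce; this step is a comparison of texts.

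| Place | Form of P2 | Consultations used? |
|---|---|---|
| Registration table | count | no |
| Protocol 7, objective | count | no |
| Protocol 7, hypothesis | rate | yes, as denominator |
| Protocol 8 | called a rate | denominator not stated |
| Protocol 20a | not specified | no |
| SAP introduction and 5.1 | count | no |
| SAP 9, model | count | not a denominator, offset or covariate |
| SAP 9, sensitivity analyses | no rate | no |

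The ratio is written out once, in Hypothesis P2, and no analysis section takes it up.

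**2. Could the rate be formed from the planned data?** Yes. SAP 6.1 lists monthly data by GP for consultations (Model 3.1) and referrals (Model 3.3). Protocol 18a gives months 1-21 for both P2 and S1. The gap is in specification, not in data collection.

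**3. When do count and rate differ?** Since referrals = rate × consultations,

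count ratio = rate ratio × consultation ratio.

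A fall in the rate by a fraction r is exactly hidden in the count when consultations rise by 1/(1 − r) − 1:

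| Fall in rate | Rise in consultations that hides it |
|---|---|
| 3% | 1/0.97 − 1 = 3.1% |
| 5% | 1/0.95 − 1 = 5.3% |
| 10% | 1/0.90 − 1 = 11.1% |
| 20% | 1/0.80 − 1 = 25.0% |

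Read the other way, rate ratio = count ratio / consultation ratio. The ratios below are assumed:

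| Count ratio | Consultation ratio | Change in rate |
|---|---|---|
| 1.00 | 0.90 | +11.1% |
| 1.00 | 0.95 | +5.3% |
| 1.00 | 1.05 | −4.8% |
| 1.00 | 1.10 | −9.1% |
| 0.95 | 0.95 | 0.0% |
| 0.95 | 1.00 | −5.0% |

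The last two rows show one count result with two different meanings for the hypothesis.

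**4. On the additive scale of the planned linear model.** The count effect is B × (rate ratio × consultation ratio − 1), where B is baseline referrals per GP-month. The documents do not give B, so 20, 40 and 80 are assumptions. With a 5% fall in the rate:

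| Consultations | Count ratio | B = 20 | B = 40 | B = 80 |
|---|---|---|---|---|
| unchanged | 0.9500 | −1.0 | −2.0 | −4.0 |
| +5% | 0.9975 | −0.05 | −0.1 | −0.2 |
| +10% | 1.0450 | +0.9 | +1.8 | +3.6 |

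The effect on the rate is the same in all three rows.

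**The case against.** The strongest reply is that the governing text is largely consistent. Protocol 20a defers to the SAP. The SAP, the registration table and the P2 objective all give the count, and the SAP states that "the statistical analysis plan has been completed prior to the completion of the data collection". On that view one hypothesis sentence is out of line, and S1, estimated with the same model, would reveal any material shift in consultations. Much of this stands: the count is the planned primary outcome, and reporting S1 limits misreading. But separate coefficients for referrals and consultations do not give a confidence interval for the rate, which needs their covariance or a direct model. The hypothesis also remains in the protocol unrevised.

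A second reply is that the rate has a denominator measured after randomisation, which the intervention may change. That also stands, and is why the rate is suggested only as support.

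Some stronger readings are tempting but unsupported:

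- *Section 8 independently defines P2 as referrals over consultations.* It says only referral rate. Taking the denominator from Hypothesis P2 is plausible, but it is an inference.
- *Protocol 20a commits to a count.* It names no outcome variable, and continuous data fits either form.
- *The primary outcome was switched from rate to count.* The registration table and the objective already give the count.
- *The numerator is undefined.* The SAP introduction and the extraction described in protocol section 12 both restrict it to secondary care. What is missing is a list of the Model 3.3 referral types that qualify.
- *The P2 result will mislead.* Nothing in the documents indicates the direction or size of any change in consultations.

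**Conclusion.** The inconsistency is certain from the text: the hypothesis is a rate, the planned outcome is a count, neither document reconciles them, and no rate analysis is planned. The hypothesis as written therefore has no planned estimate or test. This should be fixed, but it does not invalidate the planned count analysis.

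The size of the consequence is unknown. The break-even figures follow from an identity and need no baseline. The effects in referrals per GP-month rest on assumed baselines, and all the scenarios rest on assumed changes in consultations. If S1 does not change, the count and rate ratios agree and nothing is lost beyond clarity. High confidence attaches to the inconsistency, not to the harm.

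**What to change.** Before analysis:

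1. Reconcile Hypothesis P2 and protocol section 8 with SAP 5.1 and 9. Either confirm the count as primary and reword the hypothesis, or state and justify a change.
2. Prespecify a supportive rate analysis per GP-month: Model 3.3 referrals to secondary care over Model 3.1 consultations. Use either referrals per 100 consultations in a linear mixed model, or a count model with log consultations as offset. Keep the planned random effects, step effects and prior POCUS experience. SAP 6.1 and 9 describe the national trend only for remuneration codes and referrals, so include a background term only if a matching consultation trend is supplied; otherwise rely on the step effects.
3. List the Model 3.3 referral types and Model 3.1 contact types that enter the rate.
4. Correct the S1 sentence in SAP 5.2, which sets consultations before the intervention against referrals after it. Then report the count, rate and S1 effects side by side with 95% confidence intervals and interpret them together.

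The cost is SAP wording, one derived variable and one extra model. The GP-level data are already due; only a national consultation trend, if wanted, would be an additional delivery. The downside is that the denominator may itself respond to the intervention, so the rate should remain supportive and not be read alone.
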